#### 5.0 Follow-up

The clinical evaluation will be carried out at different times:

##### 5.1 Post procedural follow up

Immediately after the procedure, a multiparametric prostate MRI will be performed, followed by discharge with steroid therapy (prednisone), if not contraindicated, to be scaled and with commitments for programming the subsequent follow-up phases.

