
## 2.0 Objective of the study

With this we intend to evaluate the efficacy of the percutaneous ablative treatment with neodymium laser, that is the complete profile of safety and tolerability in acute and in the follow up, in patients suffering from Benign Prostatic Hypertrophy using, for the first time, as the main diagnostic tool in the follow-up multiparametric prostate MRI that allows us to evaluate with objective data the volume reduction of the glandular volume in the follow-up, any morphostructural gland changes and the correlation of the aforementioned advanced imaging data with the clinical data.

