## 3.0 Design of the study

Non-pharmacological interventional study in which each patient constitutes self-control. The clinical evaluation will be carried out at three different times:

Time 1: eligibility assessment, signing of informed consent

Time 2: admission, laser ablation and control with multiparametric MRI of the post-procedural prostate (T0).

Time 3 Follow up at 3 (T1) -6 (T2) -12 (T3) months from the procedure.

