#### 4.3 Technique of performing a percutaneous laser ablation treatment

The treatments will be performed by the radiology team, on an outpatient basis using the supplied Echolaser XVG combined system. The procedure will be performed with the patient in gynecological position, and in safe conditions according to the current legislation for laser treatments (such as protective glasses). Treatment includes local anesthesia of the perineal region, under ultrasound guidance. At the discretion of the medical team, sedation can be carried out with anesthetic assistance. 2 or 4 needles of 21G, 1 or 2 will be inserted in the right bumper, 1 or 2 in the left bumper. In each needle a 300 micron optical fiber will be inserted - Ditta Elesta s.r.l. - [name] - Italy, at a distance of 8-10 mm from the urethra. For each lighting, for about 6 minutes, an energy of 1800 J per fiber will be delivered, at the power of 2-3 Watts. At the end the needle and the fiber will be retracted for about 1 cm ("pull-back"). Further lighting will follow, with delivery and duration and power equal to the previous one. Depending on the size of the middle lobe one or more pull-backs can be made. In total the treatment will consist in the delivery up to 3600 J, to the power of 2-3 W for a total duration of 30 minutes. The laser causes hyperthermia, denaturation and coagulative necrosis of proteins. The maximum volume treated in a session and the extent of the ablation vary according to the prostatic volume, anatomy and receptivity of the tissue. At the end of the treatment 20 mg of Urbason ev (if not specifically contraindicated by the patient) will be administered, for anti-edema and anti-inflammatory purposes. An antibiotic, pain relief and gastroprotective therapy will also be established for 1 week. After an adequate observation period, the patient will be discharged.

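### No study contact is scheduled between discharge and the 3-month visit, so transient early post-discharge events are likely to be under-counted although the objective promises an acute safety profile

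*Combined protocol and SAP*

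**What the plan says.** **Aim.** Section 2.0 includes in the aim "the complete profile of safety and tolerability in acute and in the follow up". It does not define the acute period.

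**Procedure day.** Section 3.0 describes Time 2 as "admission, laser ablation and control with multiparametric MRI of the post-procedural prostate (T0". Section 4.3 states "The treatments will be performed by the radiology team, on an outpatient basis", and ends "After an adequate observation period, the patient will be discharged". The length and content of that observation are not given. Section 5.1 adds: "Immediately after the procedure, a multiparametric prostate MRI will be performed, followed by discharge with steroid therapy (prednisone", the steroid to be tapered, with arrangements made for the later follow-up.

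**Treatment after discharge.** Section 4.3 says: "An antibiotic, pain relief and gastroprotective therapy will also be established for 1 week".

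**Next scheduled assessment.** Section 3.0 sets "Follow up at 3 (T1) -6 (T2) -12 (T3) months from the procedure". Section 5.2 repeats these three times and lists a specialist examination, ultrasound with post-void residual, prostate MRI and a urine test. It has the IPSS and the data collection form completed at each re-evaluation. Section 9.2 collects data at the clinical evaluation and in follow-up.

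No section describes a call, visit, diary or report of unscheduled events between discharge and month 3.

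**The concern.** The aim covers acute safety, but the schedule moves from the procedure day straight to month 3. The protocol itself treats the days after discharge as clinically active, since the one-week medication course and at least the start of the steroid taper fall there. An episode of retention, bleeding, infection or pain that began and settled in that interval would not show in an examination, ultrasound, MRI, urine test or symptom score at 3 months.

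What is at stake is the credibility of any statement on early tolerability. The men are over 65 and at medium-high surgical risk, and how well they tolerate the procedure is part of the case for it. A low recorded count of early events could mean that few occurred or that few were captured, and the planned data could not separate the two. Early information not collected at the time is hard to recover later.

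The problem is when patients are observed. A precise adverse-event definition would still have no scheduled observation point before month 3.

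**Working it through.** The plan gives no event rate, capture rate or sample-size calculation, so there is no figure of its own to reproduce. The check has two parts.

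**1. Schedule set against objective**

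| Period | Scheduled study observation | Source |
|---|---|---|
| Procedure, observation, immediate MRI | Yes, observation length unstated | 3.0, 4.3, 5.1 |
| Discharge to 3 months | None | 3.0, 5.1, 5.2 |
| 3, 6 and 12 months | Examination, imaging, urine, IPSS, data form | 3.0, 5.2 |

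- Length of the gap: 365.25 / 4 = about 91 days, or 91 / 7 = 13 weeks. This is 3 / 12 = one quarter of the 12-month follow-up.
- Scheduled contacts in the gap: 0.
- Three provisions might seem to fill it, and none does. The follow-up arrangements made at discharge (5.1) concern booking the later phases. The further checks left to clinical judgment (5.2) come after the 12-month item and fix no early contact. The periodic safety updates (8.2.2) are reports to the ethics committee and do not collect events from patients.

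**2. Illustration of what incomplete capture does**

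Inputs: n = 40 (section 6.5). The true proportion of men with an early complication, p, and the share of those cases recovered at 3 months, c, are both assumptions. If each case is captured independently with probability c, the recorded rate is p × c.

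- Expected recorded cases = 40 × p × c
- Chance of recording at least one = 1 − (1 − p × c)^40

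| p | c | Expected recorded | Chance of at least one |
|---|---|---|---|
| 5% | 1.0 | 2.0 | 1 − 0.95^40 = 87.1% |
| 5% | 0.8 | 1.6 | 1 − 0.96^40 = 80.5% |
| 5% | 0.5 | 1.0 | 1 − 0.975^40 = 63.7% |
| 10% | 1.0 | 4.0 | 1 − 0.90^40 = 98.5% |
| 10% | 0.8 | 3.2 | 1 − 0.92^40 = 96.4% |
| 10% | 0.5 | 2.0 | 1 − 0.95^40 = 87.1% |

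If 0 of 40 are recorded, the one-sided 95% upper limit for the recorded rate is 1 − 0.05^(1/40) = 7.2%. The matching limit for the true rate is that figure divided by c:

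- c = 1.0: 7.2%
- c = 0.8: 0.072 / 0.8 = 9.0%
- c = 0.5: 0.072 / 0.5 = 14.4%

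**The case against.** Several points on the other side are fair.

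- **No contact at all.** A reader might infer that patients are not seen for three months. The documents show only that no study contact is scheduled. Unscheduled care is neither described nor excluded.
- **Same-day discharge.** This is an inference from the outpatient setting and from discharge following the immediate MRI. Section 3.0 speaks of admission, and the observation period has no stated length.
- **The whole acute profile is lost.** It is not. The procedure, the observation period and the immediate MRI are all observed. The gap is the early post-discharge period.
- **Events will certainly be missed, or surface only by unprompted recall.** The data collection form is not reproduced, so it may prompt for interval events. What can be said is that no recall question is described.
- **The primary endpoint is inflated.** Section 6.1 joins absence of obstructive complications and symptom improvement by an and/or, with no time window. On the 'or' reading, a man with transient retention who has improved at follow-up is a success whether or not the episode was recorded. The assessments listed there are also largely those that 5.2 schedules from 3 months. The complication component is affected only if the endpoint is read to include transient events before 3 months, which the protocol does not settle.
- **The numbers are invented.** The rates and capture shares are assumptions, and the rise from 7.2% to about 14% is simply division by 0.5. They show direction and plausible scale and are not an estimate.
- **Other safety wording is missing too.** The index lists a side-effects section (4.4) that the body lacks, and safety is not a listed endpoint in 6.1 or 6.2. That is a related but separate matter. Contacts would need a defined list of events to be interpretable, so the fix includes one.

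None of this supplies a scheduled observation between discharge and month 3.

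**Conclusion.** The point holds as a mismatch between objective and schedule. Followed exactly, the plan has no scheduled observation for about 13 weeks after discharge, and transient early post-discharge events are likely to be under-counted.

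The size of the loss is unknown. If 50% to 80% of early cases were recovered at 3 months, 20% to 50% would be lost. At an assumed true rate of 10%, that is 0.8 to 2.0 of the 4.0 cases expected in 40 men. A record of 0 of 40 would be compatible with a true rate of up to about 9.0% at 80% capture or about 14% at 50%, against 7.2% with complete capture.

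The conclusion rests on the written schedule and on the 3-month assessments describing the state at that visit. It would weaken if the data collection form already asks about events since discharge, although recall over 3 months would remain a limitation. The sponsor should make the change. The documents do not support a claim that the primary result is biased.

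**What to change.** 1. In 5.1 and 5.2, add at least one scheduled telephone contact by existing study staff soon after discharge, for example when the one-week therapy ends, with a second at about 1 month.
2. Use a fixed checklist of dated events at each contact: retention or catheter use, bleeding, fever or infection, pain, and any unplanned care. Enter the answers in the data collection form.
3. At the 3-month visit, add a prompted question on events since the last contact.
4. Report early events separately from later ones, with the early window stated in advance.
5. In 6.1, state whether transient obstructive events before 3 months count.

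If no contact is added, narrow the section 2.0 objective to safety on the procedure day and from 3 months onward.

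The cost is 40 × 1 = 40 to 40 × 2 = 80 short calls, one form page and a protocol amendment. Recorded event rates will probably look less favourable. This is data collection only, and no treatment rule changes.

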##### 5.2 Post-discharge follow-up

Specialist examination, suprapubic ultrasound of the urinary tract (with evaluation of the post-residual residue) and multiparametric prostate MRI at 3 months, 6 months and 12 months and subsequent checks according to clinical judgment.

A chemical-physical urine test and any urine culture should be attached to each clinical-ultrasound evaluation. At each reevaluation the IPSS form and the data collection form will be filled out.

## 6.0 Results and evaluation methods

### 6.1 Primary end point

Absence of obstructive complications and / or improvement of obstructive symptoms related to pre-existing benign prostatic hypertrophy to percutaneous ablative treatment with neodymium laser. The evaluation will be carried out with clinical evaluation, multiparametric prostate MRI, ultrasound of the pubic urinary tract with measurement of the post-residual residue, physical chemical examination of the urine and possibly with urine culture.

### 6.2 Secondary end points

Evaluation of the efficacy of multiparametric prostate MRI in evaluating the response to percutaneous ablative laser diode treatment of benign prostatic hypertrophy immediately after treatment and in short-term follow-up.

Quality of life assessment following percutaneous laser ablation treatment (compilation of the IPSS data sheet and data collection form).

Evaluation of the feasibility of treatment by a team of interventional radiologists.

### 6.3 Assessment methods

The evaluation will be performed according to the procedures defined in the paragraph dedicated to the follow up.

### 6.4 Statistical analysis

The descriptive analysis will be performed by calculating the central tendency, variability, symmetry and kurtosis. For categorical variables we will proceed with the construction of 2x2 contingency tables. For the inferential analysis we will proceed to the calculation of the ANOVA for repeated measures (with statistical analysis between and within), the Odds-Ratio. The result will be considered statistically significant if  $p < 0.05$ .

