#### 4.1.1 Inclusion criteria

- Age over 65 years
- Benign prostatic hypertrophy (confirmed by multiparametric prostate MRI to be performed pre-treatment)
- PSA value  $\leq 4$  ng / ml
- Indicative flow meter test for obstructive pathology
- Medium-high surgical risk.
- Presence of obstructive symptoms (voiding hesitation, intermittent mitto, reduction of urinary flow, incomplete emptying of the bladder, post-voiding incontinence and irritative symptoms such as urinary frequency, dysuria, nocturia - quantified with IPSS)
- Signature of the information sheet and of the informed consent to the treatment, to the execution of the multiparametric MRI and to the administration of the paramagnetic contrast medium.

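### Section 6.4 plans a repeated-measures ANOVA with no missed-visit rule, no sphericity correction and no confidence interval; an all-available-visits analysis with intervals would suit this 40-patient pilot better

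*Combined protocol and SAP*

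**What the plan says.** Section 3.0 describes a one-group design: "Non-pharmacological interventional study in which each patient constitutes self-control". Follow-up is at 3, 6 and 12 months.

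- **IPSS and post-void residue** have four assessments. The pre-treatment values come from sections 4.1.1 and 4.2.1, and the three later ones from section 5.2.
- **MRI volume** has five, because section 5.1 adds a scan: "Immediately after the procedure, a multiparametric prostate MRI will be performed".

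Section 6.4 is the whole statistical plan. After descriptive measures it says "For categorical variables we will proceed with the construction of 2x2 contingency tables", then names "the calculation of the ANOVA for repeated measures (with statistical analysis between and within), the Odds-Ratio" and the 0.05 threshold. It gives no missed-visit rule, sphericity correction or confidence interval, and no other section supplies one.

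The primary endpoint in section 6.1 is "Absence of obstructive complications and / or improvement of obstructive symptoms". It has no cut-off for improvement, and no visit is named as primary. Section 6.5 calls the study a pilot, gives 40 patients and says no sample-size calculation could be done.

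**The concern.** A pilot of 40 patients without a power calculation mainly offers estimates: how large the change is, what proportion succeed, and how precisely each is known. Section 6.4 plans p-values and no interval.

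The standard repeated-measures ANOVA also has two known weaknesses in this setting. It needs every visit from every patient, so one missed visit removes the patient. Its F test holds its level only under sphericity, for example when all pairs of visits are equally correlated. That is unlikely here, because the ablation falls between the first measurement and the rest. Values after treatment may resemble one another more than they resemble the pre-treatment value.

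With no rule written down, the analyst settles these matters later, possibly after seeing the data.

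**Working it through.** The documents give no effect size, SD, correlation, missing rate or success rate, so there is no planned figure to reproduce. From the documents: n = 40, k = 4 or 5 assessments, alpha = 0.05. Everything else below is assumed.

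**1. Complete cases.** If a fraction m independently misses each of v follow-up measurements, the number complete is 40 × (1 − m)^v.

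- v = 3: 40 × 0.95³ = 34.3; 40 × 0.90³ = 29.2; 40 × 0.85³ = 24.6.
- If the post-procedure MRI can also be missed (v = 4): 40 × 0.90⁴ = 26.2.

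**2. Type I error of the uncorrected F test.** The nominal df are k − 1 and (k − 1)(n − 1), so 3 and 117 for k = 4. The departure from sphericity is ε = (Σλ)² / [(k − 1)Σλ²], where λ are the variances of the orthonormal visit contrasts.

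Example with k = 4, unit variances, correlation 0.5 across the ablation and 0.9 among later visits:

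- Pre-treatment versus follow-up contrast: (9 + 8.4 − 9)/12 = 0.7.
- The two contrasts among follow-up visits: 1 − 0.9 = 0.1 each.
- ε = 0.9² / [3 × (0.49 + 0.01 + 0.01)] = 0.81/1.53 = 0.53, so the effective df are about 1.6 and 62.

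Simulated rejection rates under no change (40,000 runs per case):

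| Assumed correlation | k = 4 | k = 5 |
|---|---|---|
| Uniform, 0.5 or 0.8 | 4.9% | 4.8-5.0% |
| Serial, 0.5 to 0.9 | 5.8-7.0% | 6.2-7.9% |
| 0.4-0.6 across the ablation, 0.8-0.9 afterwards | 6.9-8.4% | 7.4-9.2% |

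The serial rows use a correlation per 3 months at months 0, 3, 6 and 12 for k = 4, and equal steps for k = 5. A more extreme pattern, 0.3 across the ablation and 0.9 afterwards, gave 9.1% and 10.4% in a smaller run of 5,000. With the Greenhouse-Geisser correction, rejection was 4.2-5.1% throughout.

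**3. Precision and bias of the 12-month mean change.** Assume SD 6, uniform correlation 0.6 and a true fall of 10 points. The variance of one patient's change is 2 × 36 × (1 − 0.6) = 28.8. At 10% missed per visit:

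- Complete cases: √(28.8/29.2) = 0.99.
- Available-case paired change: √(28.8/36) = 0.89.
- Likelihood model, simulated: 0.88.

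Now let patients whose 3-month fall is under 10 points leave from month 6 at 20/30/40%, and the others at 5%. Complete-case and available-case means are both −10.18/−10.30/−10.47. The likelihood model gives −9.99/−9.97/−10.00.

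**4. Primary proportion.** Exact (Clopper-Pearson) 95% intervals for illustrative counts are: 20/40, 34-66%; 28/40, 53-83%; 36/40, 76-97%. Counting a missed visit as not a success lowers the estimate: with 10% missed at random, a true 70% is reported as 0.70 × 0.90 = 63%.

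**5. Odds ratio.** For an illustrative table of MRI response by clinical response with cells 22, 6, 6, 6, the odds ratio is (22 × 6)/(6 × 6) = 3.7, with exact 95% interval 0.7-19.6. At this sample size it can only be exploratory.

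**The case against.** The strongest reply is that section 6.4 does not choose the weak version of the ANOVA. It names the method and is silent on incomplete patients and on correction. A reader might infer that a complete-case, uncorrected test has been specified; the text does not say so, and the losses above follow only on that reading. This stands as a limit. The reading is still reasonable, because no mixed model or correction is named.

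The second reply is that the harm is small. Under the assumptions used here, a 10-point fall with standard errors of about 0.87-1.07 is roughly 9-11 standard errors. A true error rate of 6-9% would not change that conclusion. This also stands: the size of the test matters only for an outcome with a weak effect. Available-case paired changes lose almost no precision, so the mixed model's main advantage over them is freedom from the 0.2-0.5 point bias when poorer responders leave.

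Two further inferences go beyond the documents:

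- **A before/after odds ratio cannot be estimated.** Section 4.1.1 requires "Presence of obstructive symptoms (voiding hesitation, intermittent mitto, reduction of urinary flow" and other symptoms as a list, without saying that each patient must have all of them. The difficulty arises only for a variable defined as any symptom present. A single symptom or an IPSS category can vary at entry. No section proposes the before/after contrast anyway.
- **The *between* test is invalid.** The phrase may mean only the ordinary split of variance into between-patient and within-patient parts. On that reading no group comparison is planned.

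The unnamed *between* factor, odds-ratio table and success cut-off are gaps in detail, and the point does not rest on them.

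**Conclusion.** The point holds in a limited form and should be fixed. For a one-group pilot of 40 with repeated measurements, a better analysis is available at almost no cost, and reporting the primary endpoint without an interval leaves out the main thing the study can provide.

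Read as the standard complete-case, uncorrected ANOVA, the plan keeps about 29 of 40 patients at 10% missed per follow-up visit and tests at about 6-9% under plausible non-uniform correlations. Under uniform correlation there is no inflation. All missing rates, correlations, SDs and success rates are assumptions.

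A reader might go further and conclude that the planned analysis would produce a false claim of benefit. Neither the documents nor these figures support that: a large change would remain clear under any of the analyses considered.

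**What to change.** In section 6.4:

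1. Analyse IPSS, post-void residue and MRI volume with a linear mixed model: visit as a fixed effect, unstructured within-patient covariance, Kenward-Roger df, all treated patients and all available visits. Report the mean change from pre-treatment with a 95% confidence interval at each visit. Alternatively, keep the ANOVA with Greenhouse-Geisser and add available-case paired changes with 95% intervals.
2. Report the section 6.1 endpoint as a proportion with an exact 95% interval at one visit named as primary before analysis, with the other visits supportive. Show it among all treated patients (missed visit counted as not a success) and among those observed, and note that the former is conservative.

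Minor remarks:

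- Before analysis, settle in section 6.1 whether the and/or means both or either, and what counts as improvement.
- Name the odds-ratio table and label it exploratory. MRI response by clinical response would fit the aims: section 2.0 seeks "the correlation of the aforementioned advanced imaging data with the clinical data", and section 6.2 lists "Evaluation of the efficacy of multiparametric prostate MRI in evaluating the response to percutaneous ablative laser diode treatment".
- Delete the *between* test, or tie it to one named factor.

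The cost is a few sentences, agreement on the success definition and slightly more analysis work. No new patients, visits or data are needed.
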